## PERSONNEL:

All staff and personnel associated with screening, collecting data, and analyzing data will have been trained in their laboratory and will have undergone all necessary research modules for safety and research ethics. [name] will meet with all staff on a regular basis to ensure that they are conducting research protocols appropriately. MRI data will be collected by licensed MR technicians and staff trained to analyze MRI scans. There will be regularly scheduled meetings in which study staff will review each participant with regards to the progression through the baseline sessions. During these meetings, staff will have the opportunity to discuss any participants who have safety concerns along with any questionnaire answers that may raise a red flag to certain behaviors.

Regarding use of the physical activity monitoring devices, participants will be guided through the use of the devices at the Red Visit and will be reminded repeatedly throughout the study. We will help participants through the fitting process of the device and alert them to the sound the device will make when it is properly adjusted and ready to collect data. We will ensure that participants understand how the device works and how to correctly wear it so as to avoid any discomfort or incorrect usage. We will also instruct participants to notify us if any discomfort occurs. If any discomfort does arise as a result of wearing either of the physical activity monitoring devices, we will instruct participants to discontinue use of the device.

MRI scans: To alleviate fatigue, frustration, and anxiety that might occur during the MRI scan, participants will be asked how they are feeling and will be offered breaks between cognitive tests. Participants will be able to squeeze a 'panic ball' if they become claustrophobic during the MRI scan. Doing so will stop the scan so that the participant can exit the scanner. Participants who experience claustrophobia during the scan will be withdrawn from the study. Care will be taken to minimize distress by thoroughly training all project staff who come in contact with participants, to ensure that they are sensitive to their distress and will be capable of dealing with them in a courteous manner. If a clinically significant, unexpected disease or condition is

identified during the MRI scan, we will inform the participant that they should follow-up with their personal physician for further testing, diagnosis, and prognosis information.

To address the risk of unknown ferrous materials, a standard screening instrument will be used prior to any individual entering the magnet room. This form is attached.

The MRI technologist and researchers will be able to view images of the participants' brain during the scanning session and there is a slight possibility that they incidentally detect something unusual on the MRI scans. An incidental finding is defined as a finding concerning an individual research participant that has potential health importance and is discovered in the course of conducting research but is incidental or unrelated to the study intervention or procedures. If the research team discovers an incident or abnormality (e.g., tumor) as a part of the MRI scan, it is important for the study subject to be informed (a) that these scans were not designed for clinical purposes and so a clear diagnosis and prognosis cannot be made, but (b) that if an incidental finding or abnormality is found in the scan that [name], a board certified neurologist, will assess the scan and provide feedback to the participant. If feedback to the participant is necessary, this may include the recommendation that the participant inform their personal physician about the abnormality and request follow-up procedures that are outside the purview of the research study.

MRI scans will be flagged in one of two methods:

- 1) The MR technician performing the scan at Northeastern notices a clear abnormality in the scans being collected. If the MRI technician sees something that is abnormal, they will advise [name] and other relevant staff (e.g., project coordinators), notifying them of an incidental finding. The scan will still be completed for this participant and the MR technician will refrain from informing the study participant about the possible incidental finding. The project coordinator will then start the incidental finding process. This includes:
  - i. Informing the Principal Investigator, [name], with the study ID and date of the scan.
  - ii. The imaging director at Northeastern will alert the study neuro-radiologist that a scan has been flagged and needs to be examined. All data sent to the neuro-radiologist will be de-identified.
  - iii. An Adverse Event form will be completed.
- 2) Staff notice an incidental finding while checking quality control of the data. If an incidental finding is found in this way the data manager will contact the PI ([name]), the imaging director at Northeastern (Co-I [name]) and the project coordinator who will then start the incidental finding process described above.

After examining the MRI scans, the neuro-radiologist will categorize the incidental finding into one of three categories:

1. **SERIOUS:** The participant should be notified immediately by the site PI and told to follow-up with their PCP (exclude from study).
2. **BENIGN:** The participant is informed that we found something but it is likely benign and doesn't need an immediate follow-up with their PCP

**3. NO CONSEQUENCE:** No need to evoke anxiety in the participant so there is no reason to tell them.

**Cognitive assessments:** In order to alleviate any fatigue that may occur, participants are offered breaks during testing periods. They will also be provided with a referral for psychiatric consultation upon request or if their scores on the GDS, GAI, or MoCA are clinically significant, according to each evaluation's scoring guide. Any person scoring highly on the depression, anxiety, or cognitive impairment items will be referred back to their PCP for consultation.

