#### Exclusion Criteria:

- Current or previous formal diagnosis of a DSM-V Axis I or II disorder including Major Depression (not including post-partum depression or anxiety)
- History of major psychiatric illness including schizophrenia
- Current treatment for cancer – except non-melanoma skin
- Neurological condition (MS, Parkinson's, Dementia, MCI) or brain injury (traumatic or Stroke)
- Type I Diabetes
- Type II Diabetes if unstable or controlled by insulin
- Current alcohol or substance abuse
- Current treatment for congestive heart failure, angina, uncontrolled arrhythmia, DVT or other cardiovascular condition
- A blood clot in the legs in the last 2 years
- Myocardial infarction, coronary artery bypass grafting, angioplasty or other cardiac event in the past year
- 
- Regular use of an assisted walking device or significant increase in pain when walking
- Claustrophobia (if opting into MRI)
- Not passing the Telephone Interview of Cognitive Status (TICS) as normal
- Use of any anti-psychotic, anti-depressant, anti-anxiety, and ADD/ADHD medications.
- Not fluent in English
- Contraindications to MRI (if opting into MRI)
- No regular access to a computer with internet
- Involvement in conflicting research studies currently or recently

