#### Neuroimaging:

At Yellow Visit 2, participants will either undergo neuroimaging (i.e., task fMRI, resting-state MRI, structural MRI, DWI) or complete replacement tasks at home. For the self-affirmation intervention, all participants will be shown a series of eight core values (i.e., money, creativity, religion, politics, family & friends, sense of humor, independence, spontaneity) and will be asked to choose the values they think are most and least important to them as per Cascio et al. (2016). They will proceed to fill out a simple activity sheet of questions about the value they chose (both intervention and control group versions attached). The questions will be designed to help them practice the thorough reflection required for the scanner self-affirmation task. Each participant's vision will be assessed using a Snellen chart so they can be fitted with appropriate, MRI-safe

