The data are stored on a Heroku server. Heroku’s privacy policy states that, “We take steps to protect the privacy of our customers and protect data stored within the platform. Some of the protections... include authentication, access controls, data transport encryption, HTTPS support for customer applications, and the ability for customers to encrypt stored data.” Further, answers to survey questions are stored in number form corresponding to the multiple-choice option selected, without a key to the meaning of the choice or the question itself. There is a mandatory Administrator login, requiring a username and password, to gain access to this data. Only necessary research personnel will have the login information.

We will use the Remind app to deliver links to the oTree survey via text to participants every day. Remind is a texting service primarily used by educators, students, and parents that is compliant with federal privacy laws protecting students. It has been awarded the ISO 27001:2013 certification, which is an international standard for information security

management and governance (<https://www.remind.com/blog/iso-27001-certification>). Participants will not discuss personal and/or health information through Remind, and the links sent to them will not contain private information.

Follow-up measures:

After the intervention, participants opting into the MRIs will undergo repeat neuroimaging (i.e., resting state MRI, structural MRI, task fMRI, DWI), physical assessment session, and specified cognitive tests. Additionally, in an attempt to determine the extent of benefits following the end of the formal intervention, participants will be assessed again at 3 months post-intervention, with 7 days of accelerometry recording to determine physical activity, and behavioral and psychosocial measures to assess continued cognitive benefits.

Outcome measures outside of the neuropsychological assessment battery are as follows:

Outcome measure	Type	Timeframe	Brief description
Total step count (average steps/day)	Primary	Week 0 (baseline); Week 3; Week 6; 3 Months	This metric quantifies the change in the average number of steps taken each day, from the baseline, Week 2, Week 6, and 3-month periods. It is a marker of change in habitual ambulatory activity.

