128 The DASH study is a stratified block randomized controlled trial. After reading and signing informed consent, recruited participants are randomized to either a self-affirmation plus gain-framed daily messaging group (intervention) or a loss-framed daily messaging only group (control) with a ratio of 1:1. Due to the constraints of in-person assessment during the COVID-19 pandemic, onsite participation in the MRI scans before and after the intervention is optional. Therefore, we stratify the randomization by MRI participation (yes/no) to ensure the same distribution of MRI and behavioral-only participants across the two groups. Loss-framed messages were chosen as a control group (over neutral messaging) as they provide the same contextual information as the gain-framed messages (only framed in a negative way), compared

139 to neutral messages which contain factual information (see Figure 3B for an example of gain-
140 versus loss-framed messages). All participants are informed about the randomization but blinded
141 to the group assignment. Participants are informed that the study aims to examine whether a 4-
142 week program promotes brain health and behavior. However, it is not possible to blind
143 experimenters, as they view the intervention related materials and give instructions during the
144 assessments. The randomization scheme is prepared by the Harvard Catalyst Biostatistical Group
145 using a stratified permuted block method with random blocks. All experimenters are blinded to
146 the block size. Sealed envelopes are provided to the investigator and stored at the designated site.
147 This trial is registered on clinicaltrials.gov with an identifier NCT04315363. This study received
148 ethical approval from Northeastern University Institutional Review Board (IRB).
149

150 **Participants**

151
152 We plan to recruit 80 sedentary older adults for this study between the ages of 60 and 95
153 years that engage in less than 150 minutes of moderate-to-vigorous-intensity aerobic exercise per
154 week and more than 8 hours of sitting time per day, as assessed with a self-report during an
155 initial phone screening. We plan to recruit a diverse population that is balanced across race, sex,
156 and socioeconomic status. The study is advertised via promotional flyers in and around the
157 Boston area and local senior citizen centers as well as online advertisements through websites

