158 such as Craigslist and Facebook. Potential participants are screened by phone. The Telephone
159 Interview of Cognitive Status (TICS) is used initially to screen cognitive function. Sitting Time
160 questionnaire [27] and International Physical Activity Questionnaire [28] are used for screening
161 physical activity engagement and sedentary behavior. Potential participants are asked a series of
162 questions relating to the inclusion/exclusion criteria and past medical history.
163

164 **Intervention**

165 ***Study timeline***

166 An illustration of the study timeline can be seen in Figure 1. Each participant undergoes a
167 baseline session (T1) one week before the beginning of the intervention. Informed consent is
168 obtained at baseline, during which participants specify whether they opt to participate in the MRI
169 scans or not. Randomization takes place after obtaining informed consent (T1) and participants
170 are assigned into either the intervention or control group. During the T1 visit, the participants
171 also undergo baseline testing including neuropsychological tests and neurobehavioral
172 inventories, which take about 3 hours in total. In order not to prime exercise for the baseline
173 physical activity level, inventories that are related to exercise and self-perception are not
174 administered during T1 visit. At baseline, participants wear an activPAL monitor on their thigh
175 to assess postural aspects of sedentary behavior including time spent sitting and lying and a
176 wrist-worn accelerometer on their non-dominant hand to assess physical activity (see physical
177 activity monitoring). Both monitors are worn for a week. One week later (T2), physical
178 assessments and the remaining neurobehavioral inventories related to exercise and self-
179 perception will be administrated, which takes about 1.5 hours. The intervention lasts 4 weeks,
180 during which participants receive daily intervention messages via email or smartphone.
181 Participants are fitted with the accelerometers again for a one-week mid-intervention period
182 (week 3). The post-intervention visit (T3) is scheduled at the beginning of the last intervention
183 week (week 4). After the last intervention week (T4), participants repeat the neurobehavioral
184 week (week 4). After the last intervention week (T4), participants repeat the neurobehavioral
185 week (week 4). After the last intervention week (T4), participants repeat the neurobehavioral

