214 throughout the intervention. During weeks 3 and 6, they also receive daily reminders to continue
215 wearing their accelerometers. This daily message survey setup is displayed in Figure 2. The
216 researcher's contact information is displayed on each survey page to enhance compliance. To
217 monitor the participation adherence, participants' responses are tracked and those that do not
218 complete the survey by a specified time of day are contacted the following day by research
219 assistants to prevent technical failures. The time spent on the daily message intervention
220 including the healthy messages and survey questions is recorded by the daily message system, no
221 response to the survey questions or responses under 3 seconds to the self-affirmation probe are
222 considered as non-compliance.

223
224 **Figure 2.** Messaging system setup and logic. Each participant (represented by P_x , where x designates the
225 participant number) receives their unique link. In that link, they follow a series of pages each day that
226 contains their unique questions and parameters based upon the inputted comma-separated values (CSV)
227 file. The system does not initiate until the participant begins on their first day and then repeats for 42 days
228 (4 weeks) for the duration of the daily messaging intervention. The process occurs synonymously for all
229 other participants. Links that are not activated simply remain idle until a participant is assigned that link
230

231 Measurements and materials

233 Physical activity monitoring

234 Time spent sedentary as the primary outcome will be measured with an activPAL
235 inclinometer (activPAL, PAL Technologies, Glasgow, UK). Sleep quality, duration, and physical
236 activity engagement will be measured as secondary outcomes using an GT9X Link
237 accelerometer (ActiGraph LLC, Pensacola, FL). Participants will be wearing two motion sensors
238 at week 0 (between T1 and T2), week 3 (mid-intervention), week 6 (between T3 and T4) and
239 week 14 (T5), 24 hours/day for seven continuous days (see Figure 1). To measure sedentary
240 time, an activPAL monitor is attached on the mid-anterior surface of the right thigh. This device
241 is used to measure postural aspects of sedentary behavior, including time spent lying and sitting,
242 standing, and the number of sit-to-stand transitions. An accelerometer will be worn on the non-

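### Becoming claustrophobic in an optional scan ends all study participation, so activPAL outcome data are lost avoidably in people already randomised

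*Protocol*

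**What the plan says.** Protocol section K (Risks), under Personnel, in the paragraph on MRI scans, states: "Participants who experience claustrophobia during the scan will be withdrawn from the study". The sentence refers to the study as a whole, not to the imaging part.

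Other text bears on it:

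- SAP, Study design: "onsite participation in the MRI scans before and after the intervention is optional". Randomisation is stratified by MRI participation.
- Protocol J, Neuroimaging: at Yellow Visit 2 participants are either scanned "or complete replacement tasks at home".
- SAP, Study timeline: "Randomization takes place after obtaining informed consent (T1) and participants" are then allocated to one of the two arms. Protocol J, Surveys, likewise places randomisation at the first consent visit.
- SAP, Physical activity monitoring: "Time spent sedentary as the primary outcome will be measured with an activPAL" inclinometer. Devices are worn "at week 0 (between T1 and T2), week 3 (mid-intervention), week 6 (between T3 and T4) and" week 14.
- Protocol J, Follow-up measures: after the intervention, "participants opting into the MRIs will undergo repeat neuroimaging".
- Protocol H: known claustrophobia is an exclusion for those choosing MRI. People with implanted devices unsuited to MRI may still join the remote version.
- Protocol H, remuneration: someone who cannot complete an attempted scan, with claustrophobia named as an example, is paid for it. Nothing is said there about continued follow-up.

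Neither document says that a person withdrawn under the rule goes on wearing the devices.

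**The concern.** The rule acts after randomisation, so it is not an eligibility screen. It removes people from follow-up because of an event in a component that the trial does not require and that the primary outcome does not use. Someone who declines MRI for fear of claustrophobia is followed in full. Someone who tries the scanner and becomes claustrophobic is dropped. Nothing in the design calls for that difference.

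What is at stake is avoidable missing outcome data in a trial of 80 whose planned power sits just above 80%. A person withdrawn at the first scan contributes a baseline value and nothing after it.

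**Working it through.** **1. Order of events.** Randomisation is at T1. The baseline device week lies between the Red and Orange visits (Protocol, Accelerometry), and the first scan is at Yellow Visit 2. Baseline data are therefore in hand when the first scan takes place, and all later device data are not.

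**2. What one withdrawal costs.**

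| Withdrawn at | Device weeks lost (of 4) | Time points lost in the SAP model (of 3) |
|---|---|---|
| First scan | 3: week 3, final intervention week, 3 months | 2 |
| Second scan | The 3-month week, and probably the final intervention week | 0 or 1 |

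The second row is uncertain. The protocol's timeline table seems to put the second scan ahead of the last intervention-period device week, but the table is poorly legible, and the Follow-up measures text says only that the scan comes after the intervention.

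**3. The plan's own sample size.** Inputs from the SAP, Analysis plan: difference 10.0 points, SD 14.0, two-sided alpha 0.05, power 80%, two-sample t-test, 20% drop-out.

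- The t-test needs 31.76, so 32 evaluable per arm.
- 32 / (1 − 0.20) = 40 per arm, 80 in total. The stated figure is reproduced.
- Drop-out allowance: 0.20 × 80 = 16 people.

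**4. How many people.** Neither the opt-in share nor the in-scanner claustrophobia rate is in the documents. Both are assumptions here.

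- 40 opt in, 2.5% to 10% affected: 40 × 0.025 = 1 to 40 × 0.10 = 4.
- 20 opt in, same rates: 0.5 to 2.
- Widest range tried, opt-in 25% to 100% and rate 1% to 10%: 80 × 0.25 × 0.01 = 0.2 to 80 × 1.00 × 0.10 = 8.

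**5. Data lost if 1 to 4 people leave at the first scan.**

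- Device weeks: 80 × 4 = 320 planned; 1 × 3 to 4 × 3 = 3 to 12 lost, 0.9% to 3.8%.
- Model time points: 80 × 3 = 240 planned; 1 × 2 to 4 × 2 = 2 to 8 lost, 0.8% to 3.3%.

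**6. Power.** With standard error SE = 14 × √(1/n₁ + 1/n₂) and noncentrality 10 / SE, power comes from the noncentral t distribution with n₁ + n₂ − 2 degrees of freedom. For 32 and 32: SE = 14 × √(2/32) = 3.50, noncentrality 2.857.

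| Evaluable per arm | Lost beyond the allowance | SE | Noncentrality | Power | Detectable difference at 80% power (points) |
|---|---|---|---|---|---|
| 32 / 32 | 0 | 3.500 | 2.857 | 80.3% | 9.96 |
| 32 / 31 | 1 | 3.528 | 2.834 | 79.7% | 10.04 |
| 31 / 31 | 2 | 3.556 | 2.812 | 79.0% | 10.13 |
| 30 / 30 | 4 | 3.615 | 2.766 | 77.6% | 10.30 |
| 28 / 28 | 8 | 3.742 | 2.673 | 74.7% | 10.67 |

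If the losses fall inside the 16-person allowance, the first row applies and planned power is unchanged. Four such people would then use 4/16 = 25% of the room meant for all drop-out.

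**The case against.** The strongest reply is that this is a small matter in a Stage I pilot. The plan already allows for 20% drop-out, and claustrophobia is one cause of drop-out. Known sufferers are screened out of the MRI group, so the upper rates are unsupported. The lower power figures arise only if the allowance is fully used by other causes. All of this stands, and it limits the size of the point.

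Second, the sentence is a participant-protection measure. The protocol warns that anxiety can outlast the scan, and some of these people might leave anyway. Stopping the scan is plainly right. But ending device wear and daily messages adds no protection that the protocol describes, and voluntary continuation leaves the person free to go.

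Third, the sentence may be loose wording for leaving the MRI part only, given that the payment text deals with a failed attempt scan by scan. If so, it still needs correcting, because staff will follow what is written.

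Fourth, the SAP analyses all valid data with a mixed model and imputes what is missing. That keeps earlier data and deals with the gap afterwards, but it does not replace outcomes that could have been measured. The t-test figures above are only a proxy for that model.

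Last, the scanner task delivers study content, so a person who stops midway has had partial exposure to the messages, and the home tasks are not described as a rescue after an aborted scan. This is a handling detail for the message-memory items. It is no obstacle to activPAL follow-up.

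**Conclusion.** The concern holds. As written, the rule ends outcome collection in randomised participants for an event in an optional procedure on which the primary outcome does not depend, and nothing elsewhere in the protocol or SAP narrows it.

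The consequence is some loss of precision, probably small. It ranges from no change in planned power to about 77.6% if four people are lost beyond the drop-out allowance; the widest assumptions tried (eight people) give 74.7%. These sizes rest on assumed opt-in shares and claustrophobia rates. Scan content differs by arm, so equal withdrawal in the two arms is not guaranteed, but the documents show no difference and no bias is claimed. The change is worth making because the loss is avoidable and preventing it costs almost nothing.

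**What to change.** In Protocol section K, replace the sentence with one to this effect: participants who become claustrophobic in the scanner are withdrawn from further MRI; if willing, they continue the daily messages, both activity monitors and the questionnaires in the behavioural version. Management of lasting anxiety stays with the investigator.

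In the SAP's Analysis plan, add that these participants are analysed in their randomised arm and original MRI stratum. It would help to say in the same place whether the home tasks are done after an aborted scan and how the message-memory items are scored for someone who saw only part of the scanner messages.

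The essential cost is one sentence in each document. The sample size stays at 80, and the home tasks and remote follow-up already exist.
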